Chemotherapeutic mouthrinses and toothpastes have been shown to be efficacious in helping to remove the biofilm in conjunction with manual plaque removal with toothbrushing, flossing and oral irrigation.^{4,5} This study investigated the efficacy of an over the counter (OTC) toothpaste and mouthrinse, both produced according to the FDA's CFR21 monograph for products designed to reduce supragingival plaque and gingivitis, for reducing supragingival plaque, gingivitis, and bleeding on probing. The products used in the study were ClōSYS® Sensitive Fluoride Toothpaste, which contains 0.1% stabilized chlorine dioxide (sodium chlorite in an aqueous solution) and 0.13% w/v fluoride ion, and ClōSYS® Sensitive Rinse which contains 0.1% stabilized chlorine dioxide. Early research supports the efficacy of stabilized chlorine dioxide for reducing oral biofilm.⁶ A twice daily oral hygiene regimen using both products was tested in adult subjects diagnosed with gingivitis and early periodontitis.

Objective

The purpose of the study was to evaluate the efficacy of twice daily use of CloSYS Sensitive fluoride toothpaste and Sensitive oral rinse on gingival bleeding upon probing and supragingival plaque in patients with gingivitis or periodontitis (Stage I or II).

Study Design

This was a 90-day, self-controlled, longitudinal, non-blinded clinical trial which measured changes in clinical parameters in participants with gingivitis and Stage I or II periodontitis who applied CloSYS Sensitive fluoride toothpaste twice daily with a toothbrush and CloSYS Sensitive oral rinse twice daily after brushing. Gingivitis was defined as bleeding upon probing with no loss of attachment, and periodontitis was defined when loss of periodontal tissue support through inflammation is the primary feature.

The primary response variables were Subjects' scores on the Plaque Index (PI), Gingival Index (GI) and the number of sites with bleeding upon probing (BOP). Probing depths and clinical attachment level were assessed at baseline and 3 months. Adverse events were assessed and documented at each visit. In addition, Subjects were instructed to keep a usage diary

documenting their daily use of the toothpaste and oral rinse and any comments or observations regarding usage or adverse events.

Number of Subjects

The study was conducted with 60 medically healthy participants between ages 18 to 80 years with gingivitis or periodontitis (Stage I or II) who were receiving routine preventive care and/or periodontal maintenance at the Arizona School of Dentistry & Oral Health, A.T. Still University in Mesa, Arizona.

Inclusion Criteria

The following inclusion criteria were used to determine eligibility for study participation:

- Subjects were between the ages of 18 to 80 years
- Subjects had a minimum of 20 permanent teeth, excluding third molars
- Subjects had been diagnosed with gingivitis or periodontitis (Stages I and II are based on the level of CAL and Bone Loss (BL). The diagnosis was Stage I if: (a) BL is less than 15% and (b) CAL is between 1-2mm. The diagnosis was Stage II if: (a) BL is between 15% and 33% and (b) CAL is between 3-4mm)
- Subjects exhibited bleeding upon probing in >20% of sites
- Subjects were seen every 3 months for routine dental prophylaxis/periodontal maintenance
- Subjects did not have a significant medical history or metabolic diseases (diabetes with A1C \geq 7.0, pregnancy)
- Subjects were currently non-smokers or had discontinued smoking at least 6 months prior to enrollment
- Subjects agreed to refrain from use of the following products: Peridex®, PerioGuard®, Listerine®, Cepacol®, Crest Pro-Health® rinse, Colgate Total® rinse, Colgate Total® toothpaste, Crest Pro Health® toothpaste, or any generic equivalent while participating in this study. Alcohol is not the active ingredient in any oral rinse product and does not produce a significant antibacterial effect
- Subjects were able to read and provide written informed consent
- Subjects were able to follow verbal and/or written instructions, perform oral hygiene procedures and return to the test facility for specified study examinations
- Subjects agreed not to receive a dental “cleaning” (prophylaxis) while in the study
- Subjects had to permanently reside in Arizona

Exclusion Criteria

The following criteria were used to exclude study participation:

- Subjects had significant medical history or poorly controlled/uncontrolled diabetes (as defined above)
- Subjects were pregnant
- Subjects had a medical condition that required antibiotic prophylaxis prior to dental treatment
- Subjects had taken antibiotics within 1 month of study enrollment

- Subjects who took multiple medications and/or herbal and dietary supplements known to alter bleeding and exhibits/reports spontaneous gingival bleeding
- Subjects took medications that may interfere with study results (eg. antibiotics, steroids, immunosuppressants, high dose aspirin (325+ mg/day), chemotherapy and/or radiation therapy for cancer).
- Subjects were current smokers
- Subjects had a history of non-surgical or surgical periodontal therapy within 6 months of study participation
- Subjects had Stage III or IV periodontitis, Grade B or C
- Subjects were currently taking or in the past 28 days had taken another investigational drug or participated in other investigational studies that may impact study outcomes
- Subjects had not had a dental cleaning within six months prior to the start of the study

Screening

Potential subjects were identified by the Principal Investigator (PI) following chart review and recruited by the dental hygienist during their routine preventive care (adult prophylaxis) or periodontal maintenance visit. Potential subjects were then evaluated by the PI for additional screening.

The PI reviewed patient charts to determine eligibility for potential participants in the study by eliminating those patients who did not meet the criteria for participation. All patients' periodontal status was assessed from periodontal charting and current radiographs. Only patients without active periodontal disease were considered.

Patients diagnosed with Stage I or II periodontitis who were now stable with 'reduced periodontium' and having regular periodontal maintenance were considered for inclusion. Once the clinical exam was completed and reviewed by the PI was a patient considered for acceptance into the study.

During the screening visit, every potential subject was interviewed and examined by the PI to determine eligibility according to stated inclusion/exclusion criteria. The PI explained the study procedures, with risks and benefits of participation, and the subject was given the opportunity to ask questions.

- a. Screening Interview: The Subject was asked about inclusion and exclusion criteria, demographics, smoking or non-smoking, and date of last professional dental cleaning (Appendix A: Screening Form). The following were also reviewed:
 - i. **Medical History and Medications:** A brief medical history for each subject was recorded.

At the Baseline appointment (Visit 1, Day 0), the Subject had a photograph taken of their mouth. The Gingival Index (GI) was measured first using the Modified Gingival Index (MGI).^{7,8,9} The severity of gingival inflammation was recorded from the buccal, lingual and interproximal aspects of all evaluable teeth as follows:

- Score 0 = absence of inflammation
- Score 1 = mild inflammation or with slight changes in color and texture but not in all portions of the gingival margin or papilla
- Score 2 = mild inflammation, such as the preceding criteria, in all portions of the gingival margin or papilla
- Score 3 = moderate, bright surface inflammation, erythema, edema and/or hypertrophy of the gingival margin or papilla
- Score 4 = severe inflammation: erythema, edema and/or marginal gingival hypertrophy of the unit or spontaneous bleeding, papillary congestion or ulceration

MGIs were determined by visual exam of the gingiva on 4 surfaces for each tooth present except for third molars, for a total of 28 teeth. The total number of teeth exhibiting inflammation affecting all portions of the gingival unit (Score ≥ 2) were noted at each visit. The total number of teeth affected was evaluated for each visit in the final analysis.

Next, the Plaque Index (PI) was recorded on all teeth except for third molars, as originally described by Silness and Löe.^{10,11} The PI was recorded on 4 surfaces of each tooth and scored as follows:

- Score 0 = No plaque in gingival area
- Score 1 = No plaque visible by the unaided eye, but plaque is made visible on the point of the probe after it has been moved across surface at entrance of gingival crevice.
- Score 2 = Gingival area is covered with a thin to moderately thick layer of plaque; deposit is visible to the naked eye
- Score 3 = Heavy accumulation of soft matter, the thickness of which fills out niche produced by gingival margin and tooth surface: interdental area is stuffed with soft debris

To calculate the Plaque Index (PI), the four scores were summed for each tooth, and then all scores for all of the teeth present in a subject's mouth were added to determine a total score. Then, the total score was then divided by the number of surfaces to yield the percentage plaque score used in the final analysis.

Results of the clinical indices were recorded on the approved data collection form by the PI.

Study products were then dispensed to the subject with both written and verbal instructions for use and the Diary Usage Form. Toothpaste tubes and oral rinse bottles were weighed prior to dispensing, with weights recorded on the data collection form. Dispensed products included two 32-ounce bottles of CloSYS Sensitive oral rinse and two 7-ounce tubes of CloSYS Sensitive fluoride toothpaste and disposable dosing cups. The PI provided both verbal and written oral hygiene instructions as follows:

- Clean between the teeth using dental floss or a proxy brush
- Brush with CloSYS Sensitive fluoride toothpaste for 2 minutes twice daily. Subjects were permitted to brush with either a manual or power toothbrush according to individual preference.
- After brushing, rinse with 15 mL CloSYS Sensitive oral rinse for 30 seconds, then expectorate. Do not eat or drink for 30 minutes after rinsing.

Subjects also received a Diary Usage Form with instructions to complete the form daily. Subjects documented brushing and rinsing behaviors, including the time and date for each brushing/rinsing event. Subjects were also instructed not to use any other oral care products than those given as part of the study during the entire study period. Subjects were instructed to bring back their toothpaste tubes and oral rinse bottles at each subsequent study visit along with the

Diary Usage Form. Self-reported product use and remaining product weight were used to assess compliance with the study regimen.

The subject then received an oral prophylaxis and was scheduled to return in 6 weeks for a follow-up study appointment (Visit 2).

Subjects returned for 2 additional study visits, scheduled every 45 days (Visit 2, Day 45; Visit 3, Day 90).

At Visit 2 (Day 45), subjects received photos and MGI, PI. The presence/absence of adverse events was assessed and documented. The completed Diary Usage Form and remaining products were collected, and products were weighed, with weights recorded on the data collection form. A new Diary form, one new tube of toothpaste, one new bottle of oral rinse and disposable dosing cups were dispensed with instructions to return the form and remaining products at the final study visit (Visit 3).

At Visit 3 (90 days), subjects received photos, MGI, PI, PD, CAL, BOP. Remaining products were collected and weighed, with weights recorded on the data collection form. The Diary Usage Form was also collected. The presence/absence of adverse events was assessed and documented. Subjects completed a brief survey about their product use experience and preferences (ease of use, taste, willing to continue regimen, willing to purchase).

The presence or absence of adverse events (yes/no) was documented at each study visit on the data collection form. Adverse events that occurred were described and recorded by the PI on the Adverse Events form. If indicated, photographs were taken and appropriate reporting was made to the ATSU IRB and Study Sponsor according to the study protocol and university policies.

For Visits 2 and 3, compliance was scored as a dichotomous variable (yes/no). Compliance was scored as “yes” if product weights decreased upon return and if self-reported product use according to the study protocol was completed 90% of the time as documented on the returned Diary Usage Form.

At the end of the final study visit, each subject who completed the study in its entirety was given a \$50 Amazon gift card as a reward for successful study completion.

Summary of Study Visits

- Screening exam/Consent
- Visit 1(0 Days) = Baseline
 - ✓ Updated medical history
 - ✓ Photos/Indices (MGI, PI, PD, CAL, BOP)
 - ✓ Dispensed Products
 - ✓ Provided Verbal and Written Oral Hygiene Instructions and Diary
- Prophylaxis provided by dental hygienist
- Visit 2 (45 days)
 - ✓ Updated medical history
 - ✓ Photos/Indices (MGI, PI)

- ✓ Assessed adverse events
- ✓ Collected unused product which was weighed for compliance
- ✓ Collected Diary was reviewed for compliance
- ✓ Dispensed Products and Diary
- Visit 3 (90 days)
 - ✓ Updated medical history
 - ✓ Photos/Indices (MGI, PI, PD, CAL, BOP)
 - ✓ Assessed adverse events
 - ✓ Collected unused product which was weighed and reviewed for compliance
 - ✓ Collected Diary was reviewed for compliance
 - ✓ Subject product use experience and preferences survey completed
 - ✓ Dispensed \$50 gift card reward

Removal of Subjects

Subjects were given the right to withdraw from the study at any time and for any reason without prejudice to receiving future dental care at the institution. The PI documented the withdrawal/removal from the study and the reason for withdrawal/removal in the study record. If a subject experienced a complication and wanted to withdraw, if they consented, they were scheduled for an immediate follow-up/closeout examination to determine if an adverse event was present, and if so, the causation of the adverse event was recorded. Every effort was made to follow-up with subjects who withdrew on their own from the study.

Subject data only up to the time when the subjects were withdrawn was kept but was not included in the data analysis of the study.

Off Study

Subjects were considered off study when all planned study visits, early termination, and follow-up visits were completed.

Study Outcomes

This study assessed differences in clinical outcomes at baseline, 6 and 12 weeks. The primary outcomes include changes in gingival and plaque indices (GI and PI, respectively), and bleeding on probing. Because enrolled subjects presented primarily with gingivitis, changes in pocket depth and clinical attachment level were not included in the initial data analysis, as clinically, changes observed were negligible. Secondary outcomes included adverse events, compliance with the oral hygiene regimen and patient product use experience and preferences data.

14. Hypotheses

The hypotheses for the study were as follows:

- Subjects who apply CloSYS Sensitive fluoride toothpaste and Sensitive oral rinse as directed will experience reductions in PI across time.
- Subjects who apply CloSYS Sensitive fluoride Toothpaste and Sensitive oral rinse as directed will experience reductions in GI across time.
- Subjects who apply CloSYS Sensitive fluoride Toothpaste and Sensitive oral rinse as directed will experience reductions in BOP across time.

Statistical Analysis

Data was coded and entered into an Excel spreadsheet which was then imported into IBM SPSS version 28 for analysis. Descriptive statistics were used to report demographics. The Kruskal-Wallis test, with the Dunn post-hoc test, was used to compare MGI and PI at baseline, 6 weeks and 12 weeks. Pairwise comparisons using Wilcoxon signed rank test was used to compare differences in bleeding on probing (BOP) between baseline and 12 weeks. Adverse events data, compliance data and patient product use experience data were reported using descriptive statistics. All data were de-identified and reported in aggregate form only.

REFERENCES

2. Bosshardt DD. The periodontal pocket: pathogenesis, histopathology and consequences. *Periodontol 2000*. 2018 Feb;76(1):43-50. doi: 10.1111/prd.12153. Epub 2017 Nov 30.
5. Gunsolley JC. Clinical efficacy of antimicrobial mouthrinses. *J Dent*. 2010 Jun;38 Suppl 1:S6-10. doi: 10.1016/S0300-5712(10)70004-X. Review.
8. Löe H. The Gingival Index, the Plaque Index and the Retention Index Systems. *J Periodontol*. 1967 Nov-Dec;38(6):Suppl:610-6.
9. Bessa-Rebelo M, Corrêa de Queiroz, A. Gingival Indices: State of the Art. Available at: https://www.researchgate.net/profile/Maria_Rebelo2/publication/221917002_Gingival_Indices_State_of_Art/links/544658a10cf2f14fb80f32ad/Gingival-Indices-State-of-Art.pdf Accessed January 15, 2020.

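### No section names the GI variable that was tested; the only one defined is an unscaled count of teeth at MGI ≥2 with an ambiguous surface-to-tooth rule, and the PI formula contradicts its label

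*Combined protocol and SAP*

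**What the plan says.** **Gingival index.** Study Design lists subjects' GI scores among the primary response variables. Study Outcomes says: "The primary outcomes include changes in gingival and plaque indices (GI and PI, respectively), and bleeding on probing". The second hypothesis is a reduction in GI over time.

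Study Procedures grades each site from 0 to 4. On what was collected it says: "The severity of gingival inflammation was recorded from the buccal, lingual and interproximal aspects of all evaluable teeth", and later "MGIs were determined by visual exam of the gingiva on 4 surfaces for each tooth present", giving 28 teeth as the total. It then reduces these scores to a number of teeth "exhibiting inflammation affecting all portions of the gingival unit", with score 2 or more in parentheses, and adds: "The total number of teeth affected was evaluated for each visit in the final analysis". No mean MGI or other per-subject MGI summary is defined anywhere. Statistical Analysis compares MGI at baseline, 6 and 12 weeks without saying which summary entered the test.

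**Plaque index.** Four surfaces per tooth are scored 0 to 3 and the scores are added over the mouth; then "the total score was then divided by the number of surfaces to yield the percentage plaque score used in the final analysis".

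**The concern.** A hypothesis about an index score and a count of teeth past one cut-point concern different quantities. If the count was the variable tested, the GI result describes how many teeth reach a threshold, and improvement that stays on one side of the threshold is not seen.

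The count also cannot be reproduced without a rule that turns four surface scores into one tooth status. The wording could require the whole tooth to be inflamed, hence all four surfaces. It could equally just repeat the scale's own definition, "Score 2 = mild inflammation, such as the preceding criteria, in all portions of the gingival margin or papilla", in which case a single surface scoring 2 would do.

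For plaque, the same section defines bleeding as a true percentage (bleeding sites over all sites). A reader would naturally take a percentage plaque score the same way, as the share of surfaces with plaque. The stated formula does not give that.

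**Working it through.** The documents give no figure to reproduce here, so the checks below work from the stated definitions.

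**Inputs.** From Study Procedures: MGI 0–4, 4 surfaces per tooth, 28 teeth (112 surfaces), cut at 2, PI 0–3. From Inclusion Criteria: at least 20 teeth.

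**1. What the cut registers on one surface.** There are 10 possible downward moves on a 0–4 scale. Six cross the cut (2→1, 2→0, 3→1, 3→0, 4→1, 4→0). Four do not (4→3, 4→2, 3→2, 1→0). Of the four one-step moves, only 2→1 registers.

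**2. Surface-to-tooth rule.** Give all 28 teeth the same four scores and count affected teeth under three rules: any surface ≥2, all surfaces ≥2, or tooth mean ≥2.

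| Scores on every tooth | Mean MGI | Any | All | Tooth mean |
|---|---|---|---|---|
| 2,2,1,1 | 6/4 = 1.50 | 28 | 0 | 0 |
| 2,1,0,0 | 3/4 = 0.75 | 28 | 0 | 0 |
| 2,1,1,1 | 5/4 = 1.25 | 28 | 0 | 0 |
| 1,1,1,1 | 4/4 = 1.00 | 0 | 0 | 0 |
| 4,2,1,1 | 8/4 = 2.00 | 28 | 0 | 28 |

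Going from row 1 to row 2 halves mean MGI and moves none of the counts. Going from row 3 to row 4 lowers mean MGI by 0.25/1.25 = 20%; the any-surface count falls from 28 to 0 and the other two stay at 0.

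**3. Exact bounds on mean MGI for a given count, 28-tooth mouth.** Under the any-surface rule, an affected tooth sums to 2–16 and an unaffected one to 0–4. Under the all-surface rule, the ranges are 8–16 and 0–13 (4,4,4,1).

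- Count 28: any-surface 28×2/112 = 0.50 to 28×16/112 = 4.00; all-surface 28×8/112 = 2.00 to 4.00.
- Count 0: any-surface 0 to 28×4/112 = 1.00; all-surface 0 to 28×13/112 = 3.25.

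**4. A less extreme mouth, on assumed inputs.** Suppose 30% of surfaces score ≥2.

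- Independent surfaces: any-surface 28×(1−0.7⁴) = 21.3 teeth; all-surface 28×0.3⁴ = 0.2.
- Within-tooth correlation 0.5 (beta-binomial with parameters 0.3 and 0.7): P(no surface) = (0.7×1.7×2.7×3.7)/24 = 0.495, so any-surface 28×0.505 = 14.1; P(all four) = (0.3×1.3×2.3×3.3)/24 = 0.123, so all-surface 28×0.123 = 3.5.

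Neither the 30% nor the correlation comes from the documents.

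**5. Scaling.** A count of 20 is 20/20 = 100% of teeth in one eligible subject and 20/28 = 71% in another.

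**6. Plaque.** Sum of 0–3 scores divided by number of surfaces: all surfaces at 1 gives 1.0 and all at 3 gives 3.0, so the range is 0 to 3. A mean of 1.0 over 112 surfaces is a total of 112. The fewest surfaces that reach it are 37×3 + 1×1 = 112, that is 38/112 = 34%; the most are 112×1, that is 100%.

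The choice of quantity can change ranks. Mouth A with all 112 surfaces at 1 has mean 1.0 and 100% of surfaces with plaque. Mouth B with 56 surfaces at 3 and the rest at 0 has mean 168/112 = 1.5 and 50%.

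**The case against.** A count of affected teeth is a legitimate measure of extent, and averaging ordinal grades treats the steps as equal and mixes extent with severity. That stands: mean MGI belongs beside the count and does not replace it.

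Statistical Analysis may have meant a mean MGI, since Study Procedures says the count was evaluated but not that it was the only variable or the one tested. That also stands. A reader might infer that the GI hypothesis was certainly tested by the count; the documents show only that no other summary is defined. The sections need reconciling whichever is true.

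A reader might say that the count discards most of the scale. That is so for one-step changes (3 of 4 lost) but not for downward moves overall (6 of 10 register).

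A reader might also argue that, because Study Outcomes describes mainly gingivitis subjects, the changes of interest lie in the mild range that the count partly misses. This does not follow. Study Design defines gingivitis by bleeding without attachment loss, which says nothing about MGI grade; Study Outcomes makes the remark to explain why pocket depth and attachment were left out; and no baseline MGI distribution is given.

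Finally, the bounds need extreme mouths and the worked mouths are uniform across teeth. They show that the rule must be stated, not that it changed this trial's result.

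**Conclusion.** The point holds as a mismatch of definitions affecting two primary outcomes. For GI, the only defined summary is an unscaled count at one cut-point, whose value can run from 0 to 28 for the same mouth depending on a rule the text leaves open. That it was the tested variable is inferred. The 0-to-28 contrast and the bounds are exact for 28-tooth mouths only; the 14.1 against 3.5 comparison rests on assumed inputs. No loss of power is claimed, and nothing here shows that the trial's conclusion is wrong.

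For PI, formula and label contradict each other. It is tempting to say that only the label is wrong and that the values and rank tests are unaffected. The documents do not show which half is in error. If the formula was applied as written, the label is at fault and ranks stand. If the share of surfaces with plaque was analysed, the formula is misdescribed and ranks can differ, as mouths A and B show.

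The sponsor should correct this. The repair is cheap, and without it neither variable can be interpreted with confidence.

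**What to change.** 1. Report each subject's mean MGI over all scored surfaces (0–4) alongside the tooth count. The document is written in the past tense; if the data have already been analysed, declare this analysis post hoc.
2. State the surface-to-tooth rule actually used, express the count as a percentage of teeth present, and show the result under the alternative rules (any-surface, all-surface, mean-of-surfaces) as sensitivity analyses.
3. State which plaque quantity was computed, then correct either the label, to mean PI (0–3), or the formula.
4. Name the same GI and PI variables in Study Design, Study Procedures, Study Outcomes, Hypotheses and Statistical Analysis.

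**Cost.** No new examinations: Study Procedures says severity was recorded by aspect on all evaluable teeth. The work is one extra analysis, the sensitivity results and some rewording. Items 1 and the sensitivity part of 2 are possible only if surface-level scores were kept. If only the tooth count survives, state the rule that produced it and list the lost severity information as a limitation.

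### The product-experience survey is given only at Day 90 and withdrawn subjects are left out of the analysis, so willingness to continue may be overstated if anyone left because of the products

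*Combined protocol and SAP*

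**What the plan says.** The survey appears in two places, both tied to the last visit. Study Procedures states for Visit 3 (Day 90): "Subjects completed a brief survey about their product use experience and preferences (ease of use, taste, willing to continue regimen, willing to purchase". Summary of Study Visits lists "Subject product use experience and preferences survey completed" under Visit 3 and nowhere else. The interim visit is described as "At Visit 2 (Day 45), subjects received photos and MGI, PI", followed by adverse events, diary and product weights. It has no survey.

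Study Outcomes gives the survey its standing: "Secondary outcomes included adverse events, compliance with the oral hygiene regimen and patient product use experience and preferences data". Statistical Analysis says these data are summarised descriptively, without a denominator or a rule for missing answers.

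Removal of Subjects contains four relevant statements:
- On reasons: "The PI documented the withdrawal/removal from the study and the reason for withdrawal/removal in the study record".
- On contact: "Every effort was made to follow-up with subjects who withdrew on their own from the study".
- On subjects who had a complication, wished to leave and consented: "they were scheduled for an immediate follow-up/closeout examination to determine if an adverse event was present".
- On use of the data: "Subject data only up to the time when the subjects were withdrawn was kept but was not included in the data analysis of the study".

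Number of Subjects gives 60 participants. No section gives an expected dropout rate, a count of withdrawals or a count of completers.

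**The concern.** For most survey items, losing early leavers is an ordinary missing-data problem. For willingness to continue it is more direct. A subject who leaves the study because of the taste or feel of the products has in effect answered no, so the chance of being missing depends on the answer. If such withdrawals occurred, the loss pushes the percentage in favour of the products.

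The design has no comparator arm, so there is no second group subject to the same selection against which to read the percentage. Without a stated denominator, a reader could apply figures on continuing and purchasing an over-the-counter product to everyone who started the regimen.

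What is at stake is the interpretation of one descriptive secondary outcome. The three hypotheses concern plaque index, gingival index and bleeding on probing, and none of them uses the survey.

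**Working it through.** The documents give no survey result, dropout rate or withdrawal count, so there is no figure of the plan's own to reproduce. The check has two parts: who is in the result, and how far that could move it.

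**Who is in the result**

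| Subject | Surveyed? | Other information on acceptability | In the analysis? |
|---|---|---|---|
| Attends Visit 3, still using the products | Yes | Diary, adverse event form | Yes |
| Attends Visit 3, has stopped or cut down use | Yes; the survey is not tied to compliance | Diary, adverse event form | Yes |
| Withdraws after a complication | None described | Recorded reason; closeout examination if the subject consents | No |
| Withdraws for taste or inconvenience, no complication | None described | Recorded reason; follow-up attempted, content not specified | No |

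The gap is confined to people who leave the study. For them a reason is on file, but the exclusion rule in Removal of Subjects keeps it out of the acceptability result.

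**How far the result could move**

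Inputs: N = 60 (Number of Subjects, taken here as the number enrolled). Assumed, because the documents do not give them: w withdrawals, p the willing share among the 60 − w completers, and q the share among withdrawals who would have said they were willing.

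- Reported share: p
- Share over all enrolled: [p(60 − w) + qw]/60
- Overstatement: p − [p(60 − w) + qw]/60 = (p − q)w/60

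With p = 0.90 and q = 0, the share over all enrolled is:
- w = 3: 0.90 × 57/60 = 85.5%, an overstatement of 4.5 points
- w = 6: 0.90 × 54/60 = 81%, an overstatement of 9 points
- w = 12: 0.90 × 48/60 = 72%, an overstatement of 18 points

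Overstatement in percentage points over a wider range of assumptions:

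| p | q | w = 0 | w = 3 | w = 6 | w = 12 |
|---|---|---|---|---|---|
| 0.90 | 0 | 0 | 4.5 | 9 | 18 |
| 0.90 | 0.5 | 0 | 2 | 4 | 8 |
| 0.80 | 0 | 0 | 4 | 8 | 16 |
| 0.80 | 0.5 | 0 | 1.5 | 3 | 6 |
| any | equal to p | 0 | 0 | 0 | 0 |

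The rows with q = 0 describe withdrawals that are all product-related. Rows with larger q describe a mixture of reasons.

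**Handling a mixture of reasons**

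Split w into a product-related and b other withdrawals, and let y be the number of completers who are willing. Counting the a subjects as not willing and leaving the b subjects unknown gives a lower bound of y/60 and an upper bound of (y + b)/60. For example, with a = 3, b = 3 and p = 0.90 (all assumed), y = 0.90 × 54 = 48.6 on average. The bounds are 48.6/60 = 81% and 51.6/60 = 86%, against a reported 90%.

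**The case against.** A reader might infer that acceptability is overstated as a matter of fact. The documents do not support that. They report no product-related withdrawal, and if nobody left for such a reason this bias is absent. Even with withdrawals, the effect shrinks as q approaches p.

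A reader might also infer that subjects who stopped because of the products were never asked about it. That goes too far as well. The reason for each withdrawal was recorded, follow-up of voluntary withdrawals was attempted, and anyone who stopped the products but still attended Visit 3 was surveyed. Nor is the survey the only evidence on tolerability beyond a yes/no flag: adverse events were described on a form, and the daily diary invited comments on use.

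Three further objections deserve weight. The survey is descriptive and supports no test. A well-made table would show its n anyway. And putting every enrolled subject in the denominator without more care would count someone who left for an unrelated reason as unwilling, replacing one bias with another.

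These objections limit the point to a conditional one and shape the remedy. They do not remove it. No survey is described for those who leave, the closeout examination is reserved for subjects with a complication, and the exclusion rule sets aside the recorded reasons. Nothing in Statistical Analysis commits the report to showing the denominator.

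**Conclusion.** The point holds in conditional form. Following the plan as written gives a completer-only result for a stated secondary outcome, and that result may be too favourable if any subjects withdrew for product-related reasons. Neither the presence nor the size of an overstatement can be established from the documents.

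The range of 4.5 to 18 points for 3 to 12 withdrawals rests on four assumptions: 60 is the number enrolled, every completer answered, 90% of completers were willing, and no withdrawn subject would have been. It illustrates the sensitivity and does not estimate what happened.

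This is a modest reporting point that can be settled from records the protocol says were kept. If nobody withdrew, one sentence in the report closes it.

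**What to change.** The document is written in the past tense, so the useful change is to the reporting:

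1. In Removal of Subjects, exempt the product-experience outcome from the rule that leaves withdrawn subjects' data out of the analysis. Without this, the remaining steps conflict with the plan.
2. State the number of subjects who answered the survey out of 60, and tabulate withdrawals by documented reason.
3. Report willingness to continue over all enrolled subjects. Count withdrawals documented as product-related as not willing. Show other withdrawals as missing, with best-case and worst-case bounds, so that they are not silently counted as unwilling.
4. Label ease of use, taste and willingness to purchase as completers only, with their n.

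If the plan is reused, also give the same survey at the closeout examination or during the follow-up of withdrawn subjects. The follow-up route matters, because a subject who leaves without a complication would not have a closeout examination.

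The cost is one small table and a change of denominator, using data already recorded, plus one existing form at withdrawal in any later study. The downside is a possibly less favourable percentage on a descriptive secondary outcome.
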